8.4 CONFIDENTIALITY

The Sponsor maintains confidentiality standards by coding each patient enrolled in the study through assignment of a unique patient identification number. This means that patient names are not included in data sets that are transmitted to any Sponsor location.

Patient medical information obtained by this study is confidential and may only be disclosed to third parties as permitted by the Informed Consent Form (or separate authorization for use and disclosure of personal health information) signed by the patient, unless permitted or required by law.

Medical information may be given to a patient's personal physician or other appropriate medical personnel responsible for the patient's welfare, for treatment purposes.

Data generated by this study must be available for inspection upon request by representatives of the U.S. FDA and other national and local health authorities, Sponsor monitors, representatives, and collaborators, and the IRB/EC for each study site, as appropriate.

8.5 FINANCIAL DISCLOSURE

Investigators will provide the Sponsor with sufficient, accurate financial information in accordance with local regulations to allow the Sponsor to submit complete and accurate financial certification or disclosure statements to the appropriate health authorities. Investigators are responsible for providing information on financial interests during the course of the study and for 1 year after completion of the study (i.e., last patient last visit in PML monitoring).

9. STUDY DOCUMENTATION, MONITORING, AND ADMINISTRATION

9.1 STUDY DOCUMENTATION

The investigator must maintain adequate and accurate records to enable the conduct of the study to be fully documented, including, but not limited to, the protocol, protocol amendments, Informed Consent Forms, and documentation of IRB/EC and governmental approval. In addition, at the end of the study, the investigator will receive the patient data, which includes an audit trail containing a complete record of all changes to data.

9.2 PROTOCOL DEVIATIONS

The investigator should document and explain any protocol deviations. The investigator should promptly report any deviations that might have an impact on patient safety and data integrity to the Sponsor and to the IRB/EC in accordance with established IRB/EC policies and procedures. The Sponsor will review all protocol deviations and assess whether any represent a serious breach of Good Clinical Practice guidelines and require reporting to health authorities. As per the Sponsor's standard operating procedures, prospective requests to deviate from the protocol, including requests to waive protocol eligibility criteria, are not allowed.

9.3 SITE INSPECTIONS

Site visits will be conducted by the Sponsor or an authorized representative for inspection of study data, patients' medical records, and eCRFs. The investigator will permit national and local health authorities, Sponsor monitors, representatives, and collaborators, and the IRBs/ECs to inspect facilities and records relevant to this study.

9.4 ADMINISTRATIVE STRUCTURE

This trial is sponsored by F. Hoffmann-La Roche Ltd. A CRO will be contracted to manage the study and perform monitoring activities.

Centralized facilities (vendors) will be used to collect MCS (with the exception of endoscopy data) and pMCS symptom data.

A central laboratory (i.e., Roche or a vendor) will be used for most laboratory assessments. A selected group of assessments will be performed on site or by a local laboratory.

The eCRF data will be recorded via a Sponsor-designated EDC system. An IxRS will be used for study drug inventory management and to randomize patients to study drug.

9.5 PUBLICATION OF DATA AND PROTECTION OF TRADE SECRETS

Regardless of the outcome of a trial, the Sponsor is dedicated to openly providing information on the trial to healthcare professionals and to the public, both at scientific congresses and in peer-reviewed journals. The Sponsor will comply with all requirements for publication of study results. For more information, refer to the Roche Global Policy on Sharing of Clinical Trials Data at the following website:

http://www.roche.com/roche_global_policy_on_sharing_of_clinical_study_information.pdf

The results of this study may be published or presented at scientific congresses. For all clinical trials in patients involving an IMP for which a marketing authorization application has been filed or approved in any country, the Sponsor aims to submit a journal manuscript reporting primary clinical trial results within 6 months after the availability of the respective clinical study report. In addition, for all clinical trials in patients involving an IMP for which a marketing authorization application has been filed or approved in any country, the Sponsor aims to publish results from analyses of additional endpoints and exploratory data that are clinically meaningful and statistically sound.

The investigator must agree to submit all manuscripts or abstracts to the Sponsor prior to submission for publication or presentation. This allows the Sponsor to protect proprietary information and to provide comments based on information from other studies that may not yet be available to the investigator.

In accordance with standard editorial and ethical practice, the Sponsor will generally support publication of multicenter trials only in their entirety and not as individual center data. In this case, a coordinating investigator will be designated by mutual agreement.

Authorship will be determined by mutual agreement and in line with International Committee of Medical Journal Editors authorship requirements. Any formal publication of the study in which contribution of Sponsor personnel exceeded that of conventional monitoring will be considered as a joint publication by the investigator and the appropriate Sponsor personnel.

Any inventions and resulting patents, improvements, and/or know-how originating from the use of data from this study will become and remain the exclusive and unburdened property of the Sponsor, except where agreed otherwise.

9.6 PROTOCOL AMENDMENTS

Any protocol amendments will be prepared by the Sponsor. Protocol amendments will be submitted to the IRB/EC and to regulatory authorities in accordance with local regulatory requirements.

Approval must be obtained from the IRB/EC and regulatory authorities (as locally required) before implementation of any changes, except for changes necessary to eliminate an immediate hazard to patients or changes that involve logistical or administrative aspects only (e.g., change in Medical Monitor or contact information).

Appendix 1 Open-Label Extension (Part 1, OLE) Schedule of Assessments

Part 1 (OLE)	In-Clinic Etrolizumab Administration Every 4 Weeks				At-Home Etrolizumab Administration Every 4 Weeks (or in clinic administration if unable to perform at home)				
	Clinic Visit at Every 4 Weeks, Starting at Day 1 of Week 0 (± 3 days)				Clinic Visit at Every 12 Weeks, Starting at Day 1 of Week 0 (± 3 days)	Clinic Visit at Every 48 Weeks, Starting at Day 1 of Week 0 (± 7 days)	Clinic Visit at Week 108 (-14 days)	Unscheduled Visit ^c	Early Withdrawal from Treatment Visit ^d
	0 ^{a, b}	4	8	12					
Informed consent	x								
Review eligibility criteria	x								
Vital signs (BP, pulse rate)	x			x	x	x	x		x
ECG	x					x			x
Concomitant medications	x	x	x	x	x	x	x	x	x
Adverse events ^e	x	x	x	x	x	x	x	x	x
Limited/symptom driven physical examination, including GI	x	x		x	x	x	x	x ^c	x
PML neurologic examination ^f	x			x	x	x	x	x ^c	x
Partial Mayo Clinic Score (pMCS) ^g		x	x	x	x	x		x	x ^h
Mayo Clinic Score (MCS) ⁱ							x		x ^j

Appendix 1 Open-Label Extension (Part 1, OLE) Schedule of Assessments (cont.)

Part 1 (OLE)	In-Clinic Etrolizumab Administration Every 4 Weeks				At-Home Etrolizumab Administration Every 4 Weeks (or in clinic administration if unable to perform at home)				
	Clinic Visit at Every 4 Weeks, Starting at Day 1 of Week 0 (± 3 days)				Clinic Visit at Every 12 Weeks, Starting at Day 1 of Week 0 (± 3 days)	Clinic Visit at Every 48 Weeks, Starting at Day 1 of Week 0 (± 7 days)	Clinic Visit at Week 108 (-14 days)	Unscheduled Visit ^c	Early Withdrawal from Treatment Visit ^d
	0 ^{a, b}	4	8	12					
Flexible sigmoidoscopy (or colonoscopy, IF REQUIRED) with colonic biopsies ^k							x ^l		x ^j
Pregnancy test ^m	x	x	x	x	x	x	x		x
Hematology ⁿ	x			x	x	x	x	x ^c	x ^h
Chemistry ^o	x			x	x	x	x	x ^c	x ^h
Hepatitis B DNA ^p	x			x	x	x	x		
Serum (CRP)	x					x		x ^c	x ^h
Etrolizumab administration	x	x	x	x	x	x	x		
Etrolizumab PK sample (serum) ^q	x			x		x	x		
Anti-therapeutic antibody sample (serum) ^q	x			x		x	x	x ^c	x ^h

ATA= anti-therapeutic antibody; BP = blood pressure; CRP = C-reactive protein; ECG = electrocardiogram; eCRF = electronic case report form; GI = gastrointestinal; LFT = liver function test; PK = pharmacokinetic; PML = progressive multifocal leukoencephalopathy.

Note: All assessments and blood draws are to be conducted prior study medication administration. All visit intervals based on Day 1 of Week 0.

^a Day 1 of Week 0.

^b Week 0 procedures and laboratory assessments that have been collected as part of the final visit for the Phase II OLE and Phase III controlled studies do not need to be repeated, with the exception of ATAs, which must be collected at Week 0 if the Week 0 visit occurs >7 days after the final visit of the Phase II OLE or Phase III controlled study.

Appendix 1

Open-Label Extension (Part 1, OLE) Schedule of Assessments (cont.)

- ^c Unscheduled visit represents a visit that is not as per Schedule of Assessments and is required for an adverse event or for potential relapse assessment. All indicated assessments are NOT performed at each unscheduled visit. Assessments would be symptom driven (e.g., only perform PML neurologic examination if patient reports symptoms suspected to indicate PML). pMCS to be conducted if patient experiences disease worsening and if stool frequency and rectal bleeding are available in the e-diary. Assessments corresponding to items noted in this column should be recorded on the eCRF.
- ^d Denotes the early withdrawal from treatment visit for the open-label treatment period. To be performed within 30 days of last dose of study drug. Study drug is not administered at the Early Withdrawal from Treatment visit.
- ^e Patients will be given patient alert cards that provide information regarding the signs and symptoms of PML. Patients will be instructed to contact the study site at any time if they develop any new neurological signs or symptoms suggestive of PML.
- ^f PML neurologic examination consists of the PML Subjective Checklist and the PML Objective Checklist. Administer before other assessments, as per [Appendix 5](#).
- ^g Rectal bleeding assessment+stool frequency assessment+physician's global assessment. Patients are to complete the e-diary for the stool frequency and rectal bleeding score daily during the initial 12 weeks for the pMCS. After the Week 12 visit, the stool frequency and rectal bleeding components of the pMCS (performed every 12 weeks) and MCS (for the Week 108 assessment) will be collected by the patient daily for 4 weeks prior to clinic visit. The Week 0 pMCS score is derived from data collected as part of the final visit from the Phase II OLE or the Phase III controlled studies.
- ^h Not required if unscheduled visit leads to withdrawal and assessment previously conducted at unscheduled visit.
- ⁱ Endoscopy, rectal bleeding assessment, stool frequency assessment, Physician's Global Assessment. Patients are to complete the e-diary on a daily basis for 3 weeks prior to clinic visit for the stool frequency and rectal bleeding score (for MCS).
- ^j If early withdrawal visit is prior to Week 108 visit, then flexible sigmoidoscopy/colonoscopy with biopsies and full MCS should be conducted if e-diary data are available. If early withdrawal visit is after the Week 108 visit, then flexible sigmoidoscopy/colonoscopy with biopsies should not be conducted, but pMCS should be conducted if e-diary data are available.
- ^k The flexible sigmoidoscopy/colonoscopy should be conducted on the day of the clinic visit or within 14 days prior to the clinic visit.
- ^l Each patient entered into the study will have one paired colonic biopsy sample (2 samples) taken during flexible sigmoidoscopy/colonoscopy procedure at Week 108 and placed in formalin and then paraffin embedded. The paired biopsy sample should be taken from the worst affected segment visualized (up to and including the descending colon). For patients without inflammation on endoscopy, the paired biopsy sample should be taken from the worst affected area visualized in the last endoscopy (up to and including the descending colon). In RCR consenting patients only, any residual or not entirely consumed colonic biopsy sample obtained at Week 108 will be stored in the RCR and will be destroyed no later than 15 years after the date of final closure of the associated clinical database. Original biopsy location and endoscopic depth should be clearly indicated.

Appendix 1

Open-Label Extension (Part 1, OLE) Schedule of Assessments (cont.)

- ^m For women of childbearing potential, including those who have had a tubal ligation. Perform a urine pregnancy test; if the urine pregnancy test result is positive, perform a confirmatory serum pregnancy test. Pregnancy test will be carried out at home once the patient starts etrolizumab administration at home. Patient is to report the pregnancy test result via e-diary. Patients must be reminded throughout the study that in case of a positive pregnancy test, they should stop self-administration of study drug and call the site immediately. Do not administer etrolizumab unless the serum pregnancy test result is negative.
- ⁿ Includes hemoglobin, hematocrit, platelet count, RBC count, mean corpuscular hemoglobin, mean corpuscular volume, mean corpuscular hemoglobin concentration, red cell distribution width, WBC count, and differential.
- ^o Includes sodium, potassium, chloride, bicarbonate, glucose, blood urea nitrogen, creatinine, calcium, phosphorus, magnesium, total and direct bilirubin, total protein, albumin, aspartate aminotransferase, alanine aminotransferase, lactate dehydrogenase, alkaline phosphatase, creatine phosphokinase, and uric acid.
- ^p Only enrolled patients who were hepatitis B core antibody positive in the Phase III study of origin should have hepatitis B DNA measured at these timepoints.
- ^q Samples are to be collected prior to dose administration at all timepoints indicated (see footnote “b”) and whenever serum sickness is suspected. If serum sickness or a clinically significant allergic drug reaction is suspected, the Sponsor should be notified, and serum for etrolizumab PK measurement and ATAs should be drawn and sent to the central laboratory. ATA samples may also be utilized for exploratory PD assessments or assessment of drug concentrations.

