GA27927	Phase II open-label extension study to evaluate the long-term safety of etrolizumab in patients with moderate to severe ulcerative colitis	
Patients who meet the following criteria:
 
 Patients not in safety follow-up or PML follow-up within Study GA27927 and whose last dose of etrolizumab was during the month of July 2016 may enroll in Part 1 (OLE) of Study GA28951, if eligible, and receive their first dose in this study 4 weeks after their last dose in Study GA27927
GA28948 and GA28949	
Phase III, randomized, double-blind, controlled, multicenter study to evaluate the efficacy of (induction of remission) and safety of etrolizumab compared with adalimumab and placebo in patients with moderate to severe active ulcerative colitis who are naive to TNF inhibitors
 
Treatment Arms: etrolizumab, adalimumab, placebo
	
Patients who performed the Week 10 visit who:
 
 Have not achieved clinical remission at Week 10; may receive their first dose of etrolizumab upon enrollment into Part 1 (OLE) of the OLE-SM study 2 weeks after the Week 10 timepoint in Study GA28948/GA28949 With the exception of VHP countries participating in GA28949 and Estonia (participating in GA28948): achieved clinical remission ^e at Week 10 and performed the Week 14 visit; may receive their first dose of etrolizumab upon enrollment into Part 1 (OLE) of the OLE-SM study at Week 14 in Study GA28948/GA28949 With the exception of VHP countries participating in GA28949 and Estonia (participating in GA28948): received rescue medication between Week 0 and Week 10, as defined in the GA28948 or GA28949 protocol; patients receiving rescue medication between Weeks 10 and 14 may enroll in Part 1 (OLE) of the OLE-SM study at Week 14 For VHP countries participating in GA28949 and Estonia (participating in GA28948) only: achieved clinical remission at Week 10 and performed the Week 14 visit; may receive their first dose of etrolizumab upon enrollment into Part 1 (OLE) of the OLE-SM study at Week 16 (4 weeks after the last etrolizumab/etrolizumab placebo dose in Study GA28948/GA28949)

Table 1 Eligibility Criteria for Enrollment into PART 1 of Open-Label Extension and Safety Monitoring Study (GA28951) (cont.)

Protocol Number(s)	Title	Eligibility and Timing for Enrollment a

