4.1.1 Inclusion Criteria

Part 1 (OLE)

- Patients who were previously enrolled in the Phase II OLE study or a Phase III controlled study and meet the eligibility criteria for treatment with open-label etrolizumab as described in [Table 1](#) (see Section [3.1.1.1](#)) may enroll in Part 1 (OLE) of the study. These patients must provide written informed consent and comply with the requirements of the OLE-SM protocol.

Patients not in safety follow-up or PML follow-up within Study GA27927 and whose last dose of etrolizumab is by July 2016 may enroll in Part 1 (OLE) of Study GA28951, if eligible, and receive their first dose in this study 4 weeks after their last dose in Study GA27927. On occasions where this first dose of etrolizumab cannot be administered in accordance with these requirements, the first dose of etrolizumab is to be administered with a maximum delay of 2 weeks (i.e., up to 6 weeks after their last dose of etrolizumab in Study GA27927).

Eligible patients who exit from Study GA28948 or GA28949 at Week 10 because either they did not achieve clinical remission or they required the use of rescue medication prior to the Week 10 timepoint should not receive their first dose of open-label etrolizumab in Study GA28951 until 2 weeks after the Week 10 timepoint in the Phase III controlled study to allow for adalimumab washout. The first dose of etrolizumab given to these patients entering Study GA28951 should not exceed 4 weeks following the Week 10 timepoint from the Phase III controlled study.

With the exception of VHP countries participating in GA28949 and Estonia (participating in GA28948): Patients who remain in Study GA28948 or Study GA28949 through Week 14 because they have achieved clinical remission may enroll in Part 1 (OLE) of Study GA28951 at Week 14. The first dose of open-label etrolizumab will be given on Day 1 upon enrollment into Part 1 (OLE) of Study GA28951. The first dose of etrolizumab given to the patients entering

Study GA28951 should not exceed 2 weeks following the Week 14 timepoint from the Phase III controlled study.

With the exception of VHP countries participating in GA28949 and Estonia (participating in GA28948): Eligible patients who receive rescue medication between Weeks 10 and 14 may enroll in Part 1 (OLE) of Study GA28951 at Week 14.

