4.4.1.4 Laboratory Assessments

Laboratory assessments will be performed as indicated on the Schedule of Assessments (see the Study Flowchart in [Appendix 1](#) and [Appendix 2](#)). With the exception of urine pregnancy tests, all laboratory investigations will be performed by a central laboratory. Urine pregnancy tests will be performed at specified subsequent visits or in the patient's home. If a urine pregnancy test result is positive, it must be confirmed by a serum pregnancy test.

On days of etrolizumab administration, indicated laboratory samples should be drawn prior to study drug administration. Laboratory assessments will include the following:

- Hematology (hemoglobin, hematocrit, platelet count, RBC count, WBC count, absolute count [neutrophils, eosinophils, lymphocytes, monocytes, basophils, other cells], mean corpuscular volume, mean corpuscular hemoglobin, mean corpuscular hemoglobin concentration, and red cell distribution width)
- Serum chemistries, including liver function tests (sodium, potassium, chloride, bicarbonate, glucose, blood urea nitrogen, creatinine, calcium, phosphorus, magnesium, total and direct bilirubin, total protein, albumin, alanine aminotransferase, aspartate aminotransferase, lactate dehydrogenase, alkaline phosphatase, creatine phosphokinase, and uric acid)
- C-reactive protein (CRP)
- Pregnancy test: All women of childbearing potential (including those who have had a tubal ligation) will have a urine pregnancy test performed at monthly intervals. Pregnancy tests are to be conducted at home on a monthly basis when drug administration is in the home setting and the outcome of the pregnancy test should be recorded on an e-diary. If a urine pregnancy test result is positive, it must be confirmed by a serum pregnancy test.

- Serum samples will be collected for the detection and characterization of ATAs. ATA samples will be analyzed using validated assays. ATA samples may also be utilized for exploratory PD biomarker assessments or assessment of etrolizumab concentrations.
- Serum samples will be collected for monitoring the etrolizumab concentration (PK) during the long-term dosing period. PK samples will be analyzed using validated assays.

Unless the patient gives specific consent for his or her leftover samples to be stored for optional exploratory research (see Section 4.4.1.7), biological samples will be destroyed when the final Clinical Study Report has been completed, with the following exceptions:

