5.1.1.1.2 Other Serious Infections

Background

Clinical data to date have not shown an increased risk of serious infections with etrolizumab. In the Phase II EUCALYPTUS study, serious infections were reported in 2.3% of placebo-treated patients versus none in the etrolizumab-treated patients. Nonetheless, serious infections are a potential risk due to the mechanism of action of etrolizumab, which blocks trafficking of gut-selective lymphocytes.

Patient Selection

Patients who experienced a life-threatening infection or a specific de novo or reactivated serious viral infection, such as HBV, HCV, or HIV, during the Phase II OLE or Phase III studies should not be enrolled in Part 1 of this study. Similarly, patients who developed CMV colitis leading to early treatment discontinuation in the Phase II OLE or Phase III studies should be excluded.

Patients who experienced or have an ongoing serious infection event (except for those listed below) should not receive study drug until the event has completely resolved and treatment with anti-infective medications has been completed. Patients with hepatitis B infection who test positive only for core antibody (anti-HBc +) and test negative for HBV DNA test are eligible for the study; however, these patients must undergo periodic monitoring for HBV DNA during the study.

Education, Monitoring, and Management

Patients should be monitored closely for other serious infections during the study. Patients and study staff should be informed of the possibility of increased susceptibility to infectious pathogens. Investigators will be encouraged to promptly evaluate and aggressively treat any signs and symptoms consistent with an infection.

Patients who experience a serious infection event should not receive further study drug until the event has completely resolved and treatment with anti-infective medications has been completed. All efforts should be made to identify the infectious agent. For those patients who recover from a serious infection, study medication may be restarted following consultation with the Medical Monitor.

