Appendix 2 12-Week Safety Follow-Up (Part 1, OLE) Schedule of Assessments

Part 1 (OLE)	Week (± 7 days)		Unscheduled Visit ^c
	6 ^a	12/Early Withdrawal Visit ^b	
Concomitant medications	x	x	x
Adverse events	x	x	x
Urine pregnancy test ^d		x	
Partial physical examination		x	
PK sampling (serum)		x	
Anti-therapeutic antibody sample (serum) ^e		x	
PML neurologic examination ^f		x	

ATA= anti-therapeutic antibody; PK= pharmacokinetic; PML= progressive multifocal leukoencephalopathy.

- ^a Week 6 study assessments are to be made by telephone call and not by clinic visit.
- ^b If the patient discontinues prior to completion of the 12-week safety follow-up, the indicated assessments for the 12-week safety follow-up clinic visit should be performed as the early termination visit of the safety follow-up period.
- ^c Unscheduled visit for safety monitoring.
- ^d For women of childbearing potential, including those who have had a tubal ligation, perform a urine pregnancy test; if the urine pregnancy test result is positive, confirm with a serum pregnancy test.
- ^e If serum sickness or a clinically significant allergic drug reaction is suspected, Sponsor should be notified and serum for etrolizumab PK and ATAs should be drawn and sent to the central laboratory. ATA samples may be used for PK and/or exploratory PD assessments.
- ^f PML neurologic examination consists of the PML Subjective Checklist and the PML Objective Checklist. Administer before other assessments as per [Appendix 5](#).

Appendix 3

Extended Progressive Multifocal Leukoencephalopathy Safety Monitoring (Part 2, SM) Schedule of Assessments

Part 2 (SM)	92-week Extended PML Monitoring Period ^a	
	24, 48, 68, and 92 Weeks after Patient Discontinuation from Study OR Symptom-Driven Unscheduled Telephone Call ^b OR Early Termination ^c	Unscheduled Visit ^d
PML Subjective Checklist (telephone only)	x	
PML Objective Checklist ^e		x
Adverse event reporting to the Sponsor ^f	x	x

OLE-SM= open-label extension–safety monitoring; PML = progressive multifocal leukoencephalopathy.

Note: The extended PML monitoring period is to be conducted for patients completing or discontinuing from OLE-SM Part 1 AND for patients entering OLE-SM Part 2 from blinded Phase III studies after completion of 12-week safety follow-up in the Phase III studies AND for patients entering OLE-SM Part 2 from the Phase II OLE study (GA27927).

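### Footnote p of Appendix 1 ties the only scheduled HBV DNA test to the Phase III study of origin, so any core-antibody-positive entrant from the Phase II OLE study GA27927 has no scheduled test, although Section 5.1.1.1.2 sets no such limit

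*Protocol*

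**What the plan says.** Two provisions of the current protocol deal with hepatitis B DNA in Part 1.

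- **Section 5.1.1.1.2 (Other Serious Infections, Patient Selection)** covers eligibility: "Patients with hepatitis B infection who test positive only for core antibody (anti-HBc +) and test negative for HBV DNA test are eligible". It then adds a condition: "these patients must undergo periodic monitoring for HBV DNA during the study". Neither statement mentions a parent study. The preceding paragraph of the same text, on infections that bar entry, refers to both the Phase II OLE study and the Phase III studies.
- **Appendix 1** has a hepatitis B DNA row marked at Weeks 0 and 12, the 12-weekly visits, the 48-weekly visits and Week 108. It is not marked at unscheduled or early withdrawal visits. Footnote p governs the whole row: "Only enrolled patients who were hepatitis B core antibody positive in the Phase III study of origin should have hepatitis B DNA measured".

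Section 4.4.1.4 leaves timing to the schedule ("Laboratory assessments will be performed as indicated on the Schedule of Assessments"), and its list of tests includes neither HBV DNA nor hepatitis B serology. The follow-up schedule, "Appendix 2 12-Week Safety Follow-Up (Part 1, OLE) Schedule of Assessments", has no HBV DNA row, and nor does Appendix 3.

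GA27927 patients can enter Part 1. Section 4.1.1 opens that route to "Patients not in safety follow-up or PML follow-up within Study GA27927", and the GA27927 row of Table 1 describes them as those "whose last dose of etrolizumab was during the month of July 2016". The SAP (Section 4.1.1, Baseline) names ABS4986g as the parent trial of GA27927; Protocol Section 1.3.2 describes ABS4986g as a Phase II study.

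**The concern.** A GA27927 entrant comes from the Phase II programme and has no Phase III study of origin. Read as written, footnote p cannot be met by such a patient, whatever the core antibody status. If a GA27927 entrant were positive for core antibody alone, Section 5.1.1.1.2 would call for periodic HBV DNA testing and the schedule would assign none.

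Reactivation is the risk at stake. Section 4.5.1.1 requires study drug to stop for a de novo or reactivated serious HBV infection, and the HBV DNA row is the only scheduled test specific to hepatitis B. For a patient left off that row, testing would depend on the investigator ordering it outside the schedule. A deviation check made against the schedule alone would not notice its absence, because the schedule never asked for it.

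**Working it through.** The plan gives no figure to reproduce. The check compares the texts and then counts timepoints per hypothetical patient.

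**Texts side by side**

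1. Is there a monitoring duty? Yes, in Section 5.1.1.1.2, with no restriction by parent study.
2. Where is the test scheduled? Only in the Appendix 1 row. Section 4.4.1.4 and Appendices 2 and 3 add nothing.
3. Who is assigned that row? Under footnote p, only patients core antibody positive in a Phase III study of origin.
4. Can GA27927 patients be dosed in Part 1? Yes, under Sections 1.3.1 and 4.1.1 and Table 1.
5. Do the exclusion criteria remove the relevant patients? No. Section 4.1.2 excludes de novo or reactivated serious HBV infection during the parent study, not core antibody positivity alone.

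Steps 1 to 5 together leave any core-antibody-only GA27927 entrant with a duty to be monitored and no scheduled test.

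**Timepoints per hypothetical patient**

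Inputs:
- Last GA27927 dose between 1 and 31 July 2016 (Table 1).
- First Part 1 dose 4 weeks later, or up to 6 weeks with the permitted delay (Section 4.1.1).
- Last possible dosing day 15 May 2022 (SAP Sections 1.4 and 4.1.3).
- HBV DNA at 12-weekly visits. The 48-weekly visits and Week 108 fall on multiples of 12 weeks, so they add none.

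Formula: number after Week 0 = whole part of (weeks from Day 1 to last dosing ÷ 12).

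| Case | Day 1 | Days to 15 May 2022 | Weeks | ÷ 12 | Timepoints after Week 0 |
|---|---|---|---|---|---|
| Earliest | 1 Jul 2016 + 28 days = 29 Jul 2016 | 2116 | 302.3 | 25.2 | 25 (last at Week 300) |
| Latest | 31 Jul 2016 + 42 days = 11 Sep 2016 | 2072 | 296.0 | 24.7 | 24 (last at Week 288) |

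For shorter treatment: none if off treatment before Week 12; 48 ÷ 12 = 4 through Week 48; 108 ÷ 12 = 9 through Week 108.

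Week 0 is left out because footnote b lets procedures from the parent study's final visit stand in. Counting it adds one, giving 25 to 26 for the longest stay.

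The figure of 24 to 25 depends on Table 1's wording. Sections 1.3.1 and 4.1.1 require the last GA27927 dose only by July 2016, with no earliest date. An earlier last dose moves Day 1 back, and each further 12 weeks adds one timepoint.

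**The case against.** The strongest reply is that the restriction may be deliberate. If ABS4986g and GA27927 admitted no core-antibody-positive patients, footnote p is right in practice. Appendix 1 schedules no hepatitis B serology, so antibody status has to come from the parent study, and a footnote tied to studies where it was recorded makes sense. Footnotes b and g of the same appendix name both the Phase II OLE and the Phase III studies. That can suggest an omission in footnote p, or that the authors named Phase II whenever they meant it. This reply stands as a possibility. The Phase II hepatitis B criteria are not in the documents, and the protocol nowhere says that the limit rests on them.

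The second reply is that patients are still protected. Footnote p decides who "should have hepatitis B DNA measured at these timepoints"; it neither forbids other testing nor cancels Section 5.1.1.1.2. Chemistry including ALT, AST and bilirubin is scheduled for every Part 1 patient at each visit where HBV DNA is marked, and also appears at unscheduled (if indicated) and early withdrawal visits. Hy's law reporting (Section 5.4.6.6) and adverse event collection also apply. All of this stands and limits the consequence, but the two provisions still do not match.

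A reader might go further and infer that Section 5.1.1.1.2 expressly extends monitoring to every parent study. It does not: it is silent on parent study, and the breadth is read from that silence.

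**Conclusion.** The mismatch holds and is minor. Section 5.1.1.1.2 states a monitoring requirement with no limit by parent study, while footnote p limits the only scheduled test by parent study. Any core-antibody-only, HBV-DNA-negative entrant from GA27927 is therefore off the HBV DNA schedule.

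The number of such patients is not given and may be zero. The per-patient count of 24 to 25 timepoints after Week 0 rests on a last GA27927 dose in July 2016 and dosing through to 15 May 2022. It is not an upper limit if the last dose came earlier.

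A reader might take that count as tests missed, or conclude that patients at risk of reactivation went unmonitored. The documents support neither. They do not show that any such patient enrolled, and they do not show that investigators failed to test under Section 5.1.1.1.2. The counts are timepoints that the schedule does not assign. No endpoint or planned analysis is affected.

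**What to change.** Reword the condition in footnote p to: *hepatitis B core antibody positive in the Phase II OLE or Phase III study of origin (or its parent study)*. The bracketed words are needed because antibody status for GA27927 patients may have been recorded in ABS4986g. The cost is one phrase, and the change does no harm if no such patient exists.

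Because Part 1 dosing has ended, the wording alone no longer changes anyone's care. The useful step now is to check the parent-study hepatitis B records of GA27927 entrants to Part 1. The Part 1 CSR should then state how many were core antibody positive and whether HBV DNA was measured in each, or that there were none. SAP Section 4.1.1 already plans study-conduct summaries by study of origin, so these patients are identifiable. The cost is a records check confined to that group and one sentence in the CSR, with no new samples.
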